4.8.2 Clinical Laboratory Evaluations

Laboratory evaluations are performed at Screening, Days 1, 15, 28, 42, 70-163. A subset of lab parameters that have been collected will be summarized for Period 1 (Screening, Day 1, and Day 15) and Period 2 (Days 15, 28, 42):

- Hematology: Hemoglobin, Hematocrit, WBC, Platelets
- Chemistry: Bun, Creatinine, Potassium, ALT, AST, Total Bilirubin, Alkaline phosphatase, GGT, CPK, Glucose

Change from baseline (Day 15) to Day 28 and end of Period 2 (Day 42) (and during screening and Period 1) in selected Hematology and Chemistry laboratory parameters will be summarized by dose group for all patients in the SAF population. If a Day 15 assessment is missing, the last non-missing assessment prior to Day 15 should be used. By-patient data listings will be presented and in addition, a listing of all abnormal laboratory data values will be presented.

Laboratory values for Hematology or Chemistry tests that are normally numeric, but are presented with a character string (e.g. '<1') will take the numeric value without the symbol (e.g. '<1' would be '1') for use in the analysis tables. Listings will present the original data.

- Laboratory values will be tabulated (n %) with observed value and change from baseline over time and presented by dose group.

By-patient listings of all laboratory results will be provided. These listings will report the laboratory results in SI units. Laboratory values that are clinically significantly abnormal will be identified in the data listings.

Plots of change from baseline (or percent change from baseline, as appropriate) will be provided including all pre-baseline (screening and Period 1), Period 2 baseline (Day 15) and all post-dose values for placebo and active dose groups through Period 2.

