2.2. Study Evaluations

Body weight change from baseline (as a percentage of baseline total body weight (primary endpoint) and as kg of weight loss and percent change in body mass and fat content by DEXA (secondary endpoints)) over the 4-week double-blind dosing period will be evaluated to document RM-493's effect on obesity in PWS. In addition, the effect of the randomized withdrawal on weight will be explored. It is expected that subjects will experience a minimal-modest level of weight gain during the 2 week placebo lead-in period. With initiation of double-blind 4-week RM-493/placebo treatment phase, body weight changes (reduction, lack of gain, or reduced rate of gain) will be assessed as the primary efficacy endpoint.

The safety and tolerability of RM-493 by SC injection will be assessed by comparing the frequency and severity of adverse events as well as changes in physical examinations, ECGs, [REDACTED] vital signs, laboratory evaluations and injection site reactions (see [Appendix 11.1](#)).

PWS Hyperphagia Questionnaire ([Dykens, 2014](#)) will be the primary hyperphagia-related behavior endpoint of the study, evaluated at both the end of the 4-week double-blind treatment phase, at the end of the 2-week randomized double-blind withdrawal phase, and again at the end of the open label extension. [REDACTED]

Other quality of life or behavioral measurements may also be evaluated including the Food Related Problem Questionnaire ([Russell, 2003](#)), [REDACTED] and Symptom and Global Assessments. Daily journal to quantify aberrant behavior, [REDACTED] and/or Rate of Eating measurement will also be used.

[REDACTED]

Assessment of basal metabolic rate (via VO₂ consumption) will also be measured.

Changes in symptom scores for loss of appetite will be assessed over the duration compared to placebo. All safety/tolerability and symptom scores will be compared across dose levels and with placebo lead-in phase of the study.

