For both serious and non-serious adverse events, the Investigator must determine both the intensity of the event and the relationship of the event to study drug administration. Only those injection site reactions considered clinically significant by the Investigator will be recorded as AEs.

Intensity of all AEs including clinically significant treatment-emergent laboratory abnormalities, injection site reactions and potential systemic reactions will be graded according to the CTCAE Version 4.0. The CTCAE grade refers to the severity of the AE and ranges from Grade 1 (mild AE), Grade 2 (moderate AE), Grade 3 (severe AE) and Grade 4 (life-threatening or disabling AE) to Grade 5 (death related to AE).

Adverse events not listed by the CTCAE will be graded as follows:

Mild: discomfort noticed but no disruption of normal daily activity.

Moderate: discomfort sufficient to reduce or affect daily activity.

Severe: inability to work or perform normal daily activity.

Life threatening: represents an immediate threat to life.

Relationship to study drug administration will be determined by the investigator according to the following criteria.

None: No relationship between the event and the administration of study drug. The event is related to other etiologies, such as concomitant medications or patient's clinical state.

Unlikely: The current state of knowledge indicates that a relationship to study drug is unlikely or the temporal relationship is such that study drug would not have had any reasonable association with the observed event.

Possible: A reaction that follows a plausible temporal sequence from administration of the study drug and follows a known response pattern to the suspected study drug. The reaction might have been produced by the patient's clinical state or other modes of therapy administered to the patient.

Probable: A reaction that follows a plausible temporal sequence from administration of the study drug and follows a known response pattern to the suspected study drug. The reaction cannot be reasonably explained by the known characteristics of the patient's clinical state or other modes of therapy administered to the patient.

For the purpose of safety analyses, all AEs that are classified as possible or probable will be considered treatment-related events.

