7.3. Adverse Events and Risks

Overall, RM-493 has been generally well tolerated in previous studies. Drug-Related TEAEs (for which the adverse event was assessed as possibly or probably related to study drug by the investigator) were reported in 19 of 22 (86.4%) subjects who received RM-493 and 6 of 26 (23.1%) subjects who received placebo. Below we have listed other known side effects of RM-493. Because very few studies have been done using RM-493, there may be other unknown side effects. The PIs (or a covering clinician) will be available at all times to study participants in the event of a clinical emergency. Both this availability and how to reach the investigators in an emergency will be clearly communicated orally and in writing to study participants. All study interventions will be provided free of cost.

The following side effects were fairly common with RM-493 treatment and are usually mild:

- Decreased appetite
- Nausea
- Diarrhea
- Skin discoloration/darkening
- Penile erection in males/genital discomfort and sexual arousal in females
- Vertigo
- Dry mouth
- Headache

Side effects that are less common, but could require medical attention include:

- Vomiting
- Nightmares
- Nipple disorder (rare)
- Dermal cyst (rare)

Side effects that are rare but serious include

- Anorexia
- Significant genital discomfort in females (very rare)
- Depression or sad mood (very rare)

Side effects that have not been seen in clinical trials, but will be carefully assessed in the study (see below, [Section 7.5 Guidelines for Additional Evaluations and Suspension of Dosing for a Patient](#)):

- Prolonged erections in males (>4 hours)
- Significant increases in Liver Function tests
- Cancerous changes in skin lesions

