8.5. Statistical Methods

Analyses will be based on observed data only; no data will be imputed.

Continuous efficacy endpoints will be assessed via repeated measures, longitudinal mixed analysis of variance model which will include fixed effects terms for treatment, timepoint, treatment-by-timepoint interaction, and baseline covariate, and random effect for subjects. An unstructured covariance matrix will be used to model the expected different variances among the treatments. T-tests derived from the model will use Satterthwaite's degrees of freedom estimates. The assumption of normality will be assessed via the Shapiro-Wilk statistic as a diagnostic of closeness to normality, not as a conditional test associated with efficacy endpoint analyses. Other graphical assessments of residuals from the model fit may be examined. If a substantial departure from normality is observed, a transformation such as log (post/pre) or rank may be used to analyze the data as a sensitivity analysis; however, the analysis on the original scale of observation will be reported.

The comparison of each dose of RM-493 with placebo will be carried out via 1-sided statistical test at alpha=0.05, with no adjustment for multiplicity for comparisons with two dose regimens. This is justified by the pilot nature of this small study.

AEs will be coded by using the most current version of Medical Dictionary for Regulatory Activities (MedDRA) and summarized by system organ class, preferred term, and treatment group for the number and percent of AEs reported, the number of patients reporting each AE, and the number of patients with any AE.

A by-patient AE data listing including onset and resolution dates, verbatim term, preferred term, treatment, severity, relationship to treatment, action taken, and outcome will be provided.

Safety data including laboratory evaluation and vital signs assessments will be summarized by time of collection and by treatment group. In addition, change from baseline to any post-dose values will be summarized for vital signs and clinical laboratory results. Frequency of patients with abnormal safety laboratory results will be tabulated by treatment.

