2 STUDY OBJECTIVES

2.1 Primary Objectives

After 4 weeks of double-blind study drug treatment, the primary objectives of this study are to:

[figure not shown]
- To assess safety and tolerability of RM-493
- To assess the effect of RM-493 on weight loss
- To assess the effect of RM-493 on hyperphagia-related behavior using the PWS

Hyperphagia Questionnaire

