4.8.5 ECG

ECG measurements are to be taken at screening, Day 42 and follow-up. A by-patient listing of ECG evaluations will be provided.

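### The SAP gives only listings where the protocol promised a by-treatment count of patients with abnormal laboratory results and a comparison of ECG changes

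*SAP*

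**What the plan says.** Safety and tolerability is the first-listed primary objective in both documents (SAP 2.1: "To assess safety and tolerability of RM-493").

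**Laboratory results.** Protocol 8.5 asks for summaries by time and treatment group and for change from baseline. It then adds a separate item: "Frequency of patients with abnormal safety laboratory results will be tabulated by treatment". SAP 4.8.2 keeps the first part for a named subset of haematology and chemistry analytes in Periods 1 and 2: "Laboratory values will be tabulated (n %) with observed value and change from baseline over time and presented by dose group". It also plans plots of change through Period 2. For abnormal values it says that "a listing of all abnormal laboratory data values will be presented", with clinically significant ones marked in the listings.

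**ECG.** Protocol 2.2 (and the synopsis) says that safety "will be assessed by comparing the frequency and severity of adverse events as well as changes in physical examinations, ECGs" and other items. SAP 3.3.4 names ECG evaluations as a safety endpoint. SAP 4.8.5 says: "A by-patient listing of ECG evaluations will be provided". No ECG table is described.

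**Treatment-related events.** Protocol 7.2 sets a grouping rule: "For the purpose of safety analyses, all AEs that are classified as possible or probable will be considered treatment-related events". Protocol 8.5 places relationship to treatment in a by-patient listing. The tables in SAP 4.8.1 cover TEAEs and SAEs, overall and by severity; none uses relationship.

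**The concern.** A listing shows each patient's data but makes no comparison between arms. If the SAP is followed as written, the report will show how average laboratory values moved in each dose group. It will not show how many patients in each group went outside the normal range, which is the quantity the protocol undertook to report. The protocol itself treats threshold crossing as the liver signal of interest: Protocol 7.3 lists significant liver function increases among the effects to be assessed carefully, and Appendix 11.10 works in multiples of the upper limit of normal.

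For ECGs the gap is simpler. One recording is scheduled between screening and follow-up, on Day 42, and no planned output sets it against screening by arm. At stake is how completely a primary objective is reported. The efficacy analysis is not affected.

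**Working it through.** No published figure has to be reproduced. The check sets the two documents side by side and then looks at arm size and scope.

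**Step 1. Commitment against plan.**

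| Item | Protocol | SAP | Result |
|---|---|---|---|
| Patients with abnormal laboratory results | 8.5: frequency by treatment | 4.8.2: listing | Table promised, not planned |
| Laboratory level and change | 8.5: by time and treatment group | 4.8.2: by dose group, subset, Periods 1 and 2 | Kept, with narrower scope |
| ECG change | 2.2: compared; 8.5: not named | 4.8.5: listing | Stated comparison has no analysis |
| AE relationship | 7.2: grouping rule; 8.5: listing | 4.8.1: no table | Defined category unused; no table promised |

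**Step 2. Does the n-and-percent wording in SAP 4.8.2 restore the count?** Not clearly. It is attached to observed value and change from baseline, and no abnormality category is named. SAP 4.8.3 uses the same wording for blood pressure and heart rate, where it cannot refer to laboratory abnormality.

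**Step 3. Arm sizes.** The synopsis gives about 20 patients in the first half and 16 in the second, each allocated 2:1:3. SAP 4.2 pools identical doses and all placebo.

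- Placebo: 20 × 2/6 + 16 × 2/6 = 6.7 + 5.3 = 12
- 0.5 mg: 20 × 1/6 = 3.3, about 3
- 1.5 mg: 20 × 3/6 + 16 × 1/6 = 10 + 2.7 = 12.7, about 13
- 2.5 mg: 16 × 3/6 = 8

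One abnormal patient is therefore 1/12 = 8.3%, 1/3 = 33.3%, 1/13 = 7.7% or 1/8 = 12.5% of an arm. In groups this small the finding is the number of patients, and a mean does not give it.

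**Step 4. Scope of what remains.** Protocol 6.4.8.1 lists 20 chemistry analytes; the SAP subset has 10 (BUN, creatinine, potassium, ALT, AST, total bilirubin, alkaline phosphatase, GGT, CPK, glucose). The subset is openly declared and is not in itself an error. It does mean that for the other 20 − 10 = 10 chemistry analytes, and for urinalysis, an abnormal result appears only in listings. Day 70 laboratory results also fall outside the summarised periods.

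**The case against.** The strongest reply is that little is lost.

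- SAP 4.2 summarises continuous data with median, minimum and maximum as well as mean and SD, so an extreme value in a summarised analyte would show by dose group, and there are plots. *This stands in part.* A maximum shows that someone was extreme, not how many patients were outside the range, and it covers only the subset.
- Protocol 7.2 makes any clinically relevant laboratory deterioration an adverse event, so such cases reach the TEAE tables. *This stands in part.* That route depends on the investigator's judgement of relevance; the promised table counts abnormal results.
- SAP 5 orders listings by patient within arm, so a reader could count about 36 patients by hand. *True,* but this leaves a promised tabulation to the reader.
- SAP 4 says it may not describe every analysis, and table shells are mentioned but are not among the documents. *This is a real limit.* The shells could hold such a table. The clause itself concerns supplementary work, not an analysis the protocol already specifies.
- Protocol 8.5 names laboratories and vital signs but not ECG, and heart rate is summarised under vital signs. *This stands,* and makes the ECG limb the weaker of the two.

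Two stronger readings are tempting. A reader might infer that the SAP dropped a promised table of treatment-related events. It did not: Protocol 7.2 gives only a definition, Protocol 8.5 puts relationship in a listing, and SAP 4.2 lists all raw data by default. A reader might also infer from Protocol 7.3, where drug-related TEAEs "were reported in 19 of 22 (86.4%) subjects who received RM-493 and 6 of 26 (23.1%) subjects who received placebo", that relatedness is where drug and placebo separate best. The percentages are right (19/22 = 86.4%, 6/26 = 23.1%), but that section gives no all-cause rate for comparison, and all-cause TEAEs by arm are tabulated in this trial anyway.

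**Conclusion.** The point holds in limited form. One table explicitly promised in the protocol's statistical section, the frequency of patients with abnormal laboratory results by treatment, is reduced to a listing in the SAP. One comparison stated in the protocol's evaluation section, change in ECG, is also reduced to a listing. Neither change is explained, and both bear on a primary objective.

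It would be wrong to say that safety has no comparison between arms. TEAEs and SAEs are tabulated, including by severity, and laboratory levels and changes are shown by dose group. The unused relatedness definition is a loose end and does not carry the point.

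The size is two missing by-treatment summaries in a pilot of about 36 patients; no efficacy result or error rate changes. The conclusion assumes that the unseen table shells do not already contain these tables. The arm sizes assume the planned 2:1:3 split is achieved.

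**What to change.** Before database lock:

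1. **SAP 4.8.2.** Add a table of the number and percent of patients with any abnormal post-baseline value, by analyte and treatment group. State which analytes it covers, since the protocol's sentence is not limited to the subset. Use Period 2 by dose group as the comparison and show Day 70 separately, because it is open-label. Show each denominator, since Day 28 samples exist only for patients seen in clinic. Separate newly abnormal values from those already abnormal at Day 15, because inclusion criterion 8 admits out-of-range screening results judged not clinically significant.
2. **SAP 4.8.5.** Add a screening-to-Day 42 ECG summary by treatment group: a normal/abnormal shift, or change in rate and intervals if these are recorded. Neither document says that intervals are captured, so the shift is the safer default.
3. **Optional, SAP 4.8.1.** Add TEAEs classed as possible or probable, by treatment group, so that the Protocol 7.2 definition is used.

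Alternatively, state in the SAP that items 1 and 2 are intended departures from the protocol and why. The cost is a few standard tables from data already scheduled for collection, with no new visit or assessment.

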4.8.3 Vital Signs

Vital signs measures for blood pressure (systolic and diastolic) and heart rate will be tabulated (n %) with observed value and change from baseline over time for Period 2 (Screening values and Days 15 (baseline), 28, and 42) and presented by dose group. The average of blood pressure and heart rate values for any one timepoint will be taken; if only 1 value is present for a timepoint, this value will be used in the analysis.

[figure not shown]
By-patient listings of vital signs results will be provided.

4.8.4 Physical Examinations

A by-patient listing of physical examination details will be provided; a summary table is not planned. Significant findings (new or worsening after baseline findings) from the physical examination are to be recorded as AEs.

4.8.5 ECG

ECG measurements are to be taken at screening, Day 42 and follow-up. A by-patient listing of ECG evaluations will be provided.

4.9 Pharmacokinetic Evaluation

[figure not shown]
Plasma concentrations of RM-493 will be reported separately from these analyses.

[figure not shown]
4.10 Interim Analysis

See separate iSAP

4.11 Patient Profiles

No patient profiles will be provided.

5 REPORTING OUTPUT

All outputs will be produced using SAS version 9.2 or higher. The REPORT procedure will be used to produce all tables and listings whenever possible. All statistical appendices (supportive SAS output) will be output directly from the appropriate SAS procedure.

All table and listing outputs will stand on their own by being appropriately titled, footnoted and labelled such that the contents of their output are clear without reference to other study documents. All outputs will contain a footer indicating the name of the program used to produce the output and the date and time the output was generated; pages will be numbered 'x of y'. The block of information containing notes, footnotes, and listing/table/figure generation will be flush with the bottom margin.

Tables, listings, and figures will be numbered according to ICH Guidelines E3, Structure and Content of Clinical Study Reports.

All tables, listings, and statistical appendices will be produced to landscape orientation and will be incorporated into a Word document (margins 1.5" at the top and 1" at the left, right, and bottom) using Courier New 8 point font or higher.

All adverse event and concomitant medication listings will contain relative study days for the start and end dates of events being reported in addition to the actual dates and times of the events. Day 1 is the day study drug is administered. Day -1 is the day immediately preceding Day 1; there is no Day 0 in this study. Formulae for calculating the relative study days are provided in Table 1.

Unless indicated otherwise in the shells, listings of efficacy data will contain the relative time for the evaluation. The formula for calculating the relative time is provided in Table 1.

Listings will include all patients with data relevant to the particular listing and will be ordered by patient and visit within each treatment arm

Unless specified otherwise, percentages will be based on the number of non-missing observations (which will not always be the same as the number of patients in the treatment arm). The header will contain the number of patients in the treatment arm.

All percentages will be rounded and reported to a single decimal point (xx.x%) except for a percentage of 100% which will be reported as 100%. A value of 0% will be reported as a blank.

Analyses that include P values will report the P value to 3 decimal places with a leading zero (e.g., 0.023). P values <0.0005 will be reported as <0.001 not 0.000; p-values greater than 0.9995 will be reported as >0.999 not 1.000.

Unless it is not practical, mean and median values will be formatted to one more decimal place from the measured value. The standard deviation will be formatted to two more decimal places than the measured value. Minimum and maximum values will be presented with the same number of decimal places as the measured value. The number of decimal places in the measured value will not necessarily be reflected in the table and listing shells.

6 APPENDICES

Appendix 1: Schedule of Assessments

Study Period	Screening	Onset Single-Blind Treatment Run-in	Double Blind Treatment		End Double Blind / Onset Withdrawal Period	End Withdrawal / Onset Optional Open Label Extension	End Open Label Extension	Post-Study Follow Up
Study Day	Days -30 to -1	Days 1-14	Days 15-41		Days 42-55	Days 56-69		Days 90 to 163 ²⁴
Procedure		Run-In Day 1 ⁶	Onset Treatment Period Day 15±2-	Treatment Period Interim Visit ~Day 28 ^{4,6}	Treatment Period End, Onset Withdrawal Day 42±2	Onset Optional Expansion ~Day 56±2	Final Visit Day 70 -2 or +4	Follow up Visit
Informed consent	X							
Inclusion/Exclusion review	X	X ⁵						
Medical history review	X	X ⁵	X ¹⁵					
Pregnancy test	X	X ⁵	X ^{15, 26}		X	X		X
Physical examination ¹	X		X ¹⁵		X			X
Height	X							
Comprehensive skin exam ²	X							X
<hr/>								
Fitzpatrick scale ⁷	X							
<hr/>								
Weight	X	X ⁵	X ¹⁵	X ²³	X	X	X	X
DEXA			X ²²		X ²²		X	
Archive sample for storage ¹¹		X ⁵			X		X	
Single-Blind placebo practice		X						
Randomization to treatment ³			X ³					
Study treatment administration ¹²		X	X ⁶	X ^{6,23}	X ⁶	X	X	
Injection site inspection ¹³		X	X	X ²³	X	X	X	X
Vital signs ¹⁴	X	X ⁵	X ¹⁵	X ²³	X	X	X	X
ECG (12-lead) ¹⁶	X				X ¹⁶			X
Safety laboratory tests ¹⁷	X		X ¹⁵	X ²³	X		X	X
Questionnaires/Assessments		X ⁵	X ¹⁵	X	X	X	X	X

